10.8. Appendix 8: Values of Potential Clinical Importance

10.8.1. Laboratory Values

Clinical Chemistry			
Laboratory Parameter	Units	Clinical Concern Range	
		Low Flag	High Flag
Albumin	g/L	< 30 g/L	> 55 g/L
Aspartate Aminotransferase	IU/L		\ge 3x ULRR
Alanine Aminotransferase	IU/L		\ge 3x ULRR
Bilirubin (total)	μmol/L		\geq 2x ULRR
Calcium (albumin corrected)	mmol/L	< 1.87 mmol/L	> 2.56 mmol/L
Phosphate	mmol/L	< 0.81 mmol/L	> 1.77 mmol/L
Potassium (serum)	mmol/L	> 0.5 mmol/L below LLRR	> 1.0 mmol/L above ULRR

Hematology			
Laboratory Parameter	Units	Clinical Concern Range	
		Low Flag	High Flag
Platelet Count	GI/L	< 80 GI/L	> 500 GI/L
Leukocytes (white blood cell count)	GI/L	< LLRR	> 5x ULRR
Neutrophils	GI/L	< 0.5x LLRR	
Lymphocytes	GI/L	< 0.5x LLRR	

Iron Parameters			
Laboratory Parameter	Units	Clinical Concern Range	
		Low Flag	High Flag
Ferritin	ng/mL	< 100 ng/mL	> 800 ng/mL
TSAT	%	<15%	> 40%

Other PCI Values					
Laboratory Parameter Units Clinical Concern Range					
		Low Flag	High Flag		
iPTH	ng/L		> 9x ULRR		

10.8.2. Vital Signs

Vital Sign Parameter	Units	Clinical Concern Range		
(Absolute)		Lower Upper		
Systolic Blood Pressure	mmHg	\leq 85 mmHg	\geq 180 mmHg	
Diastolic Blood Pressure	mmHg	\leq 45 mmHg	\geq 110 mmHg	

200807

Vital Sign Parameter	Units	Clinical Concern Range		
(Absolute)		Lower	Upper	
Heart Rate	bpm	\leq 40 bpm	≥ 110 bpm	
Notes:				
 At visits where BP and HR are assessed in triplicate, the average of the 3 values will be used to assess PCI criteria. 				

• For subjects who undergo in-clinic dialysis, the post-dialysis BP and HR values will be used to assess PCI criteria, unless otherwise specified.

200807

10.9. Appendix 9: Multicenter Studies

10.9.1. Methods for Handling Centres

• In this multicentre global study, enrolment will be presented by investigative site, country, and the regions.

Region	Countries ²
Region 1: Asia Pacific	India, Malaysia ¹ , Republic of Korea ¹ , Singapore ¹ , Taiwan ¹
Region 2: Eastern Europe/South Africa	Bulgaria, Turkey, Czech Republic, Estonia, Hungary, Poland, Romania, Russian Federation, Ukraine, South Africa ¹
Region 3: Western Europe/Canada/ANZ	Australia ¹ , Austria, Belgium, Canada ¹ , Denmark ¹ , France, Germany, Greece, Italy, Netherlands ¹ , New Zealand ¹ , Norway ¹ , Portugal, Spain ¹ , Sweden ¹ , United Kingdom ¹
Region 4: Latin America	Argentina, Brazil ¹ , Mexico
Region 5: USA	USA ¹

NOTES:

[1]: Countries which will collect the EQ-5D-5L and EQ VAS.

[2] Countries that do not participate or do not randomize any subjects will be removed from the regional grouping.

For any summaries which include information related to a subject's center or investigator, the most recent center and investigator at the time that the database is final will be used.

200807

10.10. Appendix 10: Examination of Covariates, Subgroups & Other Strata

10.10.1. Handling of Covariates, Subgroups & Other Strata

- The following is a non-exhaustive list of covariates that may be used in summaries of demographics, descriptive summaries and statistical analyses.
- Additional covariates of clinical interest may also be considered.
- If the percentage of subjects is small within a particular subgroup, then the subgroup categories may be refined prior to unblinding the trial.
- If the category cannot be refined further, then descriptive rather than statistical comparisons may be performed for the particular subgroup. If there are less than 25 subjects in one of the subgroup categories, any subgroup statistical comparison should be interpreted with caution.
- A pre-specified strategy for prioritizing subgroups/covariates is defined below (as recommended in the 2015 draft Committee for Medicinal Products for Human Use (CHMP) guidance on the investigation of subgroups in confirmatory clinical trials)
- The co-primary and principal secondary endpoints will be evaluated for the subgroups below. Although subgroup analyses are aimed to assess for consistency with the overall results, they may have low power, especially if the subgroup is small or has a low number of events. Statistical models (Cox Proportional Hazards or ANCOVA) will be adjusted for the covariates used in the original analysis, subgroup, treatment and treatment by subgroup interaction. For the prognostic randomization stratification factors (region and dialysis type), the actual status of the factor derived from the eCRF will be used (see Section 10.10.2). Note that for the cardiovascular risk score covariate, the above model will not include a term for dialysis type as this analysis is restricted to HD patients only. For the subgroup Regions combined (USA vs. non-USA), the randomization stratification factor Region (with 5 levels, Regions 1- 5) will not be included in the statistical model.
- For subgroup analyses of time-to-event endpoints, point estimates and confidence intervals for the rate per 100 person-years will be reported for each treatment group within a subgroup, as well as the point estimate and two-sided 95% CI for the difference in rates between treatments within a subgroup. For within-group rates, the two-sided 95% CI will be obtained using an exact Poisson method. For difference in rates between treatments, the two-sided 95% CI will be constructed with a Normal approximation using Wald's method [Liu, 2006].
- For Hgb and selected PRO endpoints using MMRM model in the original analysis, the statistical model for the corresponding subgroup analyses will have the following factors: dialysis type, region, baseline value, baseline value by time, and subgroup by treatment by time interaction terms. The model will be run without main effects (treatment, visit, and subgroup) and two-way interaction terms (subgroup by time, treatment by time, and subgroup by treatment) for computational ease since in SAS,

the main effects and two-way interaction terms are included within the three-way interaction term, thus giving equivalent result. For the selected Hgb, BP, and PRO endpoints using MMRM in the original model that contain only main effects and two-way interaction terms, both the main effects and the two-way interaction terms will be included in the model statement. If any of the above MMRM models encounter convergence issues, then the following steps will be performed in this sequence:

- Step 1: Use Fisher scoring method
 - Scoring=0 will be used as the first option, which is equivalent to no scoring, and if the model fails to converge, the scoring will be updated to scoring=1
 - The scoring will be updated each time the model fails to converge until a maximum of scoring=4 is reached. At this point, if the model fails to converge, Step 2 will be utilized.
- Step 2: If the model fails to converge, instead of unstructured, TOEPH variance-covariance matrix will be used in conjunction with Step 1
- Step 3: If the model fails to converge, denominator degrees of freedom will be changed from Kenward-Roger to Residual in conjunction with Steps 1 and 2.

Please note that if any of the models still fail to converge after Step 3, model-adjusted analyses will not be performed. The associated descriptive statistics will be displayed. If the original model fails to converge, but it converges after one of the three steps, the output will display the changes made to the original model in a footnote.

- When a subgroup category assesses the same or a similar parameter (e.g., country is similar to region) as one of the prognostic stratification variables, the randomization stratification variable will be removed from the model.
- Point estimates and two-sided 95% CIs will be estimated within subgroups, the subgroup by treatment interaction two-sided p-value will be calculated and subgroup results will be graphically presented (e.g. Forest Plots). Directional consistency in subgroup treatment effects and a non-significant interaction p-value (two-sided 10% level) would support that the overall treatment effect is broadly applicable to the full study population. Subgroup analyses will not be adjusted for multiplicity.
 - In addition, a nominal one-sided non-inferiority p-value using a non-inferiority margin of -0.75 g/dL and a nominal one-sided superiority p-value will be generated for the difference between treatment groups for each level of the hyporesponder subgroup analyses of the co-primary Hgb endpoint.

Category	Covariates and / or Subgroups	Summary of Demographics & Baseline Characteristics Note: Include 'Missing' categories, if applicable.	Subgroup Analysis for Co-primary MACE & Principal Secondary Safety Endpoints Note: Do not include 'Missing' categories.	Subgroup Analysis for Co-primary Hgb & Principal Secondary Efficacy Endpoints Note: Do not include 'Missing' categories.
Key Covariates/Subgroup	s of Regulatory/Clinical Interest or Potential	Biological Plausibility	y for Different Subgroup Ef	fects
Age (years)	Summary statistics of continuous values	Yes	No	No
Age at randomization (Grouping 1)	< 65 years, 65-<75 years, ≥75 years	Yes	Yes	Yes
Age at randomization (Grouping 2)	\leq 18 years, 19 - 64 years, \geq 65 years	Yes	No	No
Age at randomization (Grouping 3)	18-64 years, 65 - 84 years, ≥ 85 years	No (included in stand-alone age ranges table)	No	No
Gender	Female, Male	Yes	Yes	Yes
Ethnicity	Hispanic or Latino, Not Hispanic or Latino	Yes	Yes	Yes
High level race	American Indian or Alaskan Native Asian Black or African American Native Hawaiian or Other Pacific Islander White Mixed Race	Yes	Yes	Yes
Race detail	American Indian or Alaskan Native	Yes	No	No

Category	Covariates and / or Subgroups	Summary of Demographics & Baseline Characteristics Note: Include 'Missing' categories, if applicable.	Subgroup Analysis for Co-primary MACE & Principal Secondary Safety Endpoints Note: Do not include 'Missing' categories.	Subgroup Analysis for Co-primary Hgb & Principal Secondary Efficacy Endpoints Note: Do not include 'Missing' categories.
	Asian – Central/South Asian Heritage Asian – East Asian Heritage Asian – Japanese Heritage Asian – South East Asian Heritage Black or African American Native Hawaiian or Other Pacific Islander White – Arabic/North African Heritage White – White/Caucasian/European Heritage Mixed Asian Race Mixed White Race Mixed Race			
Region	See Region categories defined in Section 10.9.1	Yes	Yes	Yes
Regions combined	USA, Non-USA	Yes	Yes	Yes
Country	See Countries listed in Section 10.9.1	Yes	No	No
Dialysis type at randomization ¹	HD, PD, Missing (repeat using HD - conventional, HDF/HF, PD, Missing)	Yes	Yes (HD/PD only)	Yes (HD/PD only)
Prior ESA type at randomization	Darbepoetin alfa only, Epoetin only, Methoxy PEG-epoetin beta only,	Yes	No	No

Category	Covariates and / or Subgroups	Summary of Demographics & Baseline Characteristics Note: Include 'Missing' categories, if applicable.	Subgroup Analysis for Co-primary MACE & Principal Secondary Safety Endpoints Note: Do not include 'Missing' categories.	Subgroup Analysis for Co-primary Hgb & Principal Secondary Efficacy Endpoints Note: Do not include 'Missing' categories.
	Multiple, Missing			
Standardized prior ESA dose (U/week) ²	Summary statistics of continuous values	Yes	No	No
Standardized prior ESA dose group ²	< 7,000 U/week, ≥7,000 U/week, Missing	Yes	Yes	Yes
Baseline erythropoietin resistance index (ERI) (U/kg/wk/g/L)	Summary statistics of continuous values	Yes	No	No
Baseline ERI quartiles	Overall ITT Population Quartile 1: <xx U/kg/wk/g/L Overall ITT Population Quartile 2: xx - <xx g="" kg="" l
Overall ITT Population Quartile 3: xx - <xx g="" kg="" l
Overall ITT Population Quartile 4: ≥ xx U/kg/wk/g/L Missing</xx></xx></xx 	Yes	No	No
rhEPO hyporesponder ²	No, Yes, Missing	Yes	Yes	Yes
Standardized Prior ESA Dose (U/week) for rhEPO Hyporesponders	Summary statistics of continuous values	Yes	No	No

Category	Covariates and / or Subgroups	Summary of Demographics & Baseline Characteristics Note: Include 'Missing' categories, if applicable.	Subgroup Analysis for Co-primary MACE & Principal Secondary Safety Endpoints Note: Do not include 'Missing' categories.	Subgroup Analysis for Co-primary Hgb & Principal Secondary Efficacy Endpoints Note: Do not include 'Missing' categories.
Standardized Prior ESA Dose (U/week) for rhEPO Non- hyporesponders	Summary statistics of continuous values	Yes	No	No
Alternate definition of rhEPO hyporesponder Definition 2 ²	No, Yes, Missing	Yes	No	No
Alternate definition of rhEPO hyporesponder Definition 3 ²	No, Yes, Missing	Yes	No	No
Baseline Hgb (g/dL)	Continuous covariate for Hgb co- primary analysis; summary statistics of continuous values	Yes	No	No
Baseline Hgb group	<pre>< 9 g/dL, 9- <10 g/dL, 10-11 g/dL, > 11 g/dL, Missing</pre>	Yes	Yes	Yes
Baseline post-dialysis body mass index (kg/m ²)	Summary statistics of continuous values	Yes	No	No
Baseline post-dialysis body mass index group	<30 kg/m², ≥30 kg/m², Missing	Yes	Yes	Yes
Baseline post-dialysis weight (kg)	Summary statistics of continuous values	Yes	No	No
Baseline post-dialysis weight group	<75 kg, ≥75 kg, Missing	Yes	No	No
Baseline post-dialysis weight	Overall ITT Population Quartile 1: < xx	Yes	Yes	Yes

Category	Covariates and / or Subgroups	Summary of Demographics & Baseline Characteristics Note: Include 'Missing' categories, if applicable.	Subgroup Analysis for Co-primary MACE & Principal Secondary Safety Endpoints Note: Do not include 'Missing' categories.	Subgroup Analysis for Co-primary Hgb & Principal Secondary Efficacy Endpoints Note: Do not include 'Missing' categories.
quartiles	kg Overall ITT Population Quartile 2: xx kg - < xx kg Overall ITT Population Quartile 3: xx kg - < xx kg Overall ITT Population Quartile 4: ≥xx kg Missing			
Baseline hsCRP (mg/L)	Summary statistics of continuous values	Yes	No	No
Baseline hsCRP group	≤3 mg/L, >3 mg/L, Missing	Yes	No	No
Baseline hsCRP quartiles	Overall ITT Population Quartile 1: < xx	Yes	Yes	Yes
Standardized prior ESA dose (U/week) for baseline hsCRP	Summary statistics of continuous values	Yes	No	No

Category	Covariates and / or Subgroups	Summary of Demographics & Baseline Characteristics Note: Include 'Missing' categories, if applicable.	Subgroup Analysis for Co-primary MACE & Principal Secondary Safety Endpoints Note: Do not include 'Missing' categories.	Subgroup Analysis for Co-primary Hgb & Principal Secondary Efficacy Endpoints Note: Do not include 'Missing' categories.
Overall ITT Population Quartile 1: < xx mg/L				
Standardized prior ESA dose (U/week) for baseline hsCRP Overall ITT Population Quartile 2: xx -< xx mg/L	Summary statistics of continuous values	Yes	No	No
Standardized prior ESA dose (U/week) for baseline hsCRP Overall ITT Population Quartile 3:xx - < xx mg/L	Summary statistics of continuous values	Yes	No	No
Standardized prior ESA dose (U/week) for baseline hsCRP Overall ITT Population Quartile 4: >= xx mg/L	Summary statistics of continuous values	Yes	No	No
Dosing algorithm at randomization	Original algorithm, Updated algorithm	Yes	No	Yes (Hgb only)
Other Exploratory Covariates/S	Subgroups where Biological Plausibility	/ for Heterogeneous E	ffects Are Not Known or A	nticipated
CV risk score for HD subjects	Low risk (Overall ITT Population Tertile 1: < xx), Medium risk (Overall ITT Population Tertile 2: xx - < xx), High risk (Overall ITT Population	Yes	Yes	No

Category	Covariates and / or Subgroups	Summary of Demographics & Baseline Characteristics Note: Include 'Missing' categories, if applicable.	Subgroup Analysis for Co-primary MACE & Principal Secondary Safety Endpoints Note: Do not include 'Missing' categories.	Subgroup Analysis for Co-primary Hgb & Principal Secondary Efficacy Endpoints Note: Do not include 'Missing' categories.
	Tertile $3: \ge xx$) (Note: only defined for HD subjects See Section 10.6.2 for details.)			
Dialysis vintage at screening	0 - <2 years, 2-<5 years, ≥5 years, Missing	Yes	Yes	Yes
History of diabetes	No, Yes, Missing	Yes	Yes	Yes
History of stroke	No, Yes, Missing	Yes	Yes	Yes
History of MI	No, Yes, Missing	Yes	Yes	Yes
History of cancer	No, Yes, Missing	Yes	Yes	Yes
History of heart failure	No, Yes, Missing	Yes	Yes	Yes
History of thromboembolic events	No, Yes, Missing	Yes	Yes	Yes
Hospitalization within 6 months prior to screening	No, Yes, Missing	Yes	Yes	Yes
Transfusion within 6 months prior to screening	No, Yes, Missing	Yes	Yes	Yes
Baseline iron use	No iron use IV iron use only Oral iron use only Other iron use only IV and oral iron use only	Yes	No	No

Category	Covariates and / or Subgroups	Summary of Demographics & Baseline Characteristics Note: Include 'Missing' categories, if applicable.	Subgroup Analysis for Co-primary MACE & Principal Secondary Safety Endpoints Note: Do not include 'Missing' categories.	Subgroup Analysis for Co-primary Hgb & Principal Secondary Efficacy Endpoints Note: Do not include 'Missing' categories.
	IV and other iron use only Oral and other iron use only IV, oral and other iron use			
Standardized baseline IV iron dose (mg/month)	Continuous covariate for monthly IV iron dose analysis, summary statistics of continuous values	Yes	No	No
Standardized baseline IV iron dose (mg/month) for subjects using IV iron at baseline	Continuous covariate for monthly IV iron dose analysis, summary statistics of continuous values	Yes	No	No
Baseline post-dialysis SBP (mmHg)	Continuous covariate for change from baseline in SBP analysis, summary statistics of continuous values	Yes	No	No
Baseline post-dialysis DBP (mmHg)	Continuous covariate for change from baseline in DBP analysis, summary statistics of continuous values	Yes	No	No
Baseline post-dialysis MAP (mmHg)	Continuous covariate for change from baseline in MAP analysis, summary statistics of continuous values	Yes	No	No
Dialysis access type used at randomization	Arteriovenous fistula Arteriovenous graft Central venous catheter – tunneled Central venous catheter – non-	Yes	No	No

Category	Covariates and / or Subgroups	Summary of Demographics & Baseline Characteristics Note: Include 'Missing' categories, if applicable.	Subgroup Analysis for Co-primary MACE & Principal Secondary Safety Endpoints Note: Do not include 'Missing' categories.	Subgroup Analysis for Co-primary Hgb & Principal Secondary Efficacy Endpoints Note: Do not include 'Missing' categories.
	tunneled Peritoneal catheter Other Missing			
ACEI/ARB use at randomization	No, Yes	Yes	Yes	Yes
Phosphate binder use at randomization	Iron-based phosphate binders Calcium-based phosphate binders Non-calcium and non-iron based phosphate binders No phosphate binder use	Yes	No	No
Vitamin D use at randomization	No, Yes	Yes	No	No
Baseline Kt/V urea for HD subjects	Summary statistics of continuous values	Yes	No	No
Baseline Kt/V urea for PD subjects	Summary statistics of continuous values	Yes	No	No
Baseline URR for HD subjects (%)	Summary statistics of continuous values	Yes	No	No
History of cardiovascular disease	No, Yes	Yes	Yes	No
Beta blockers use at	No, Yes	Yes	No	No

Category	Covariates and / or Subgroups	Summary of Demographics & Baseline Characteristics Note: Include 'Missing' categories, if applicable.	Subgroup Analysis for Co-primary MACE & Principal Secondary Safety Endpoints Note: Do not include 'Missing' categories.	Subgroup Analysis for Co-primary Hgb & Principal Secondary Efficacy Endpoints Note: Do not include 'Missing' categories.
randomization				
SGLT2i use at randomization	No, Yes	Yes	No	No
Statin use at randomization	No, Yes	Yes	No	No
Aspirin use at randomization	No, Yes	Yes	No	No
Vitamin K antagonist use at randomization	No, Yes	Yes	No	No
Insulin use at randomization	No, Yes	Yes	No	No
Calcimimetics use at randomization	No, Yes	Yes	No	No
Diabetic medication use at randomization	No, Yes	Yes	No	No
Baseline estimated dry weight (kg)	Summary statistics of continuous values	Yes	No	No

NOTES:

1: Subjects who change dialysis modalities during the study will be counted in the subgroup corresponding to their dialysis modality at randomization.

2: Prior ESA dose standardization and ESA hyporesponsiveness are defined in Section 10.6.2. Supportive definitions of hyporesponders will be included in the summary of demographics and baseline characteristics, but will not be used in subgroup analyses.

200807

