1. REPORTING & ANALYSIS PLAN SYNOPSIS

Overview	Key Elements of the RAP
Purpose	• This RAP describes the planned analyses and outputs required for the final Clinical Study Report (CSR) for study 200807.
Protocol	• This RAP is based on the fifth protocol amendment of study 200807 [GlaxoSmithKline Document Number 2015N226659_07, 30JUL2020]. While there is also a France-specific fifth protocol amendment [GlaxoSmithKline Document Number 2015N226659_08, 30JUL2020], the analyses described in the France-specific amendment are consistent with the analyses described in the global protocol amendment.
Co-Primary Objectives	To compare daprodustat to rhEPO for hemoglobin (Hgb) efficacy (non- inferiority)
	 To compare daprodustat to rhEPO for cardiovascular (CV) safety (non- inferiority)
Co-Primary Endpoints	Mean change in Hgb between baseline and evaluation period (EP, mean over Weeks 28 to 52)
	 Time to first occurrence of adjudicated major adverse cardiovascular event (MACE); [composite of all-cause mortality, non-fatal myocardial infarction (MI) or non-fatal stroke]
Study Design	• This is a randomized, open-label (sponsor blind), active-controlled, parallel- group, multi-center, event-driven study in dialysis subjects with anemia associated with chronic kidney disease (CKD) who are currently treated with erythropoiesis stimulating agents (ESAs). ESAs refer to any rhEPO or methoxy PEG-epoetin beta.
	• This study will comprise 4 study periods: a 4-week screening period, a 4-week placebo run-in period, a treatment period, and a follow-up period. Prior ESA therapy continues during the screening and run-in periods.
	• The total duration of the study is dependent upon the accumulation of at least 664 adjudicated first MACE (i.e., it is event-driven) unless review of interim data by the Independent Data Monitoring Committee (IDMC) recommends bringing the study to an earlier close.
	• Subjects will be stratified by dialysis type, by region and by participation in the ambulatory blood pressure monitoring (ABPM) sub-study. Dialysis type and region are considered to be stratification factors that are potentially prognostically important, i.e., predictive of study endpoints while participation in the ABPM sub-study is an administrative stratification factor intended solely to ensure a similar number of sub-study subjects in each of the two randomized groups.

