	 Following stratification, subjects will be randomized 1:1 to receive oral daprodustat or rhEPO [intravenous (IV) epoetin alfa or subcutaneous (SC) darbepoetin alfa].

Overview	Key Elements of the RAP
	• Both treatment arms (daprodustat and rhEPO) will follow a protocol-specified randomized treatment dose adjustment algorithm to achieve and/or maintain Hgb within the target range of 10-11 g/dL inclusive. Dose changes will be made programmatically by the Interactive Response Technology (IRT) system for both randomized treatment arms.
Planned Analyses	• It is planned that study unblinding will occur after at least 664 first MACE have occurred (see Section 3.2). Planned final analyses will be performed after study unblinding.
	 An IDMC will review safety and efficacy data periodically from ongoing clinical trials in the daprodustat clinical development program for the treatment of subjects with anemia associated with chronic kidney disease.
	 In addition, an interim analysis is planned for this study which will assess whether the daprodustat program has met criteria for futility or harm and whether the study should be stopped. The IDMC will review the interim analysis results and will provide a recommendation regarding early stopping to the sponsor.
Key Analysis Populations	• The primary population for the Hgb efficacy and MACE safety analyses will be the All Randomized Intent-to-Treat (ITT) population. Subjects will be analyzed according to the treatment to which they were randomized.
Co-Primary Hypotheses	• The co-primary Hgb efficacy objective will assess the estimand defined as the effect of daprodustat treatment relative to rhEPO on the change in Hgb from baseline to the average of all values in the EP, regardless of adherence to treatment including interruptions and discontinuations, the use of non-randomized ESA medication for any reason including rescue therapy, or the use of blood transfusions in subjects on dialysis currently treated with an ESA with anemia secondary to CKD and assuming subjects do not die before the end of the EP. The analysis will test whether daprodustat is non-inferior to rhEPO according to the following statistical hypotheses:
	 Null: The difference in mean change in Hgb between baseline and EP, between treatment arms (daprodustat -rhEPO), is less than or equal to -0.75 g/dL.
	 Alternative: The difference in mean change in Hgb between baseline and EP, between treatment arms (daprodustat -rhEPO), is greater than -0.75 g/dL.

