8.1.1.2. Planned Principal Secondary Efficacy Statistical Analyses

Principal Secondary Efficacy Statistical Analyses: Average Monthly IV Iron Dose
Endpoint(s)

• Average monthly IV iron dose (mg)/subject to Week 52

Model Specification

- Average monthly IV iron dose (mg)/subject from baseline to Week 52 will be determined by calculating the total IV iron dose per subject from treatment start date + 1 to the earliest of (Week 52 visit date, first blood (RBC or whole blood) transfusion date, and treatment stop date + 1 day) which corresponds to the time while the subject was on randomized treatment and before receiving a blood transfusion. This total IV iron dose will be divided by (the number of days from treatment start date + 1 to the earliest of (Week 52 visit date, first blood transfusion date (RBC or whole blood), and treatment stop date +1) /30.4375 days). See Section 10.4.1 for the definition of on-treatment IV iron.
- An ANCOVA model will be used to compare the difference in average monthly IV iron dose per subject between arms, adjusting for:
 - o Treatment
 - Baseline monthly IV iron dose (see Section 10.5.2)
 - Dialysis type (as randomized, see Section 10.10.2)
 - Region (as randomized, see Section 10.9 & Section 10.10.2)

200807

20001
Principal Secondary Efficacy Statistical Analyses: Average Monthly IV Iron Dose
Model Results Presentation
 The number and percentage of subjects with baseline IV iron use, on-treatment EP IV iron use, and on-treatment IV iron use to Week 52 will be summarized by treatment. Average monthly IV iron dose at baseline, while on treatment during the EP, and while on
treatment to Week 52 will be summarized by treatment group using mean, standard deviation, minimum, P25, median, P75, and maximum.
 The least square (LS) mean estimates and standard errors by treatment group, LS mean difference, two-sided 95% CI and one-sided superiority p-value for the difference in average monthly IV iron dose/subject to Week 52 between the daprodustat and rhEPO arms from the ANCOVA model will be presented. The number of subjects contributing to the analysis and the associated mean and standard deviation of the baseline and Week 52 values will also be displayed with the results of the ANCOVA model.
• A listing of average monthly IV iron dose will be provided including treatment, site ID, unique subject ID, time period, and average monthly IV iron dose at Week 52.
Model Results Interpretation
See Section 10.11.1.

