10.10.2. Randomization Stratification

Randomization is stratified by dialysis type (HD or PD), region and by participation in an ABPM sub-study to ensure balance across treatment groups for both the overall parent study and within the ABPM sub-study. The prognostic stratification factors (i.e., dialysis type and region) will be taken into account within the analysis models. Stratification by ABPM sub-study participation was implemented for logistical reasons, and will not be taken into account within analysis models.

Baseline dialysis type strata will be identified by two data sources:

- PPD's IRT dataset
- eCRF

The proposed approach is to use the IRT strata in the adjusted analysis models in order to provide a randomization-based test statistic in accordance with the principle of 'analyze as randomized'. In summaries of subgroups however, the actual status of the factor for stratification derived from the eCRF form will be used. Additionally, subjects who change dialysis modality during the study will remain in the dialysis modality strata that was assigned at randomization.

200807

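### The USA versus non-USA subgroup models leave differences among the four non-USA randomization regions unadjusted, so the Hgb and IV iron intervals are conservative to the extent that region is prognostic

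*SAP*

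**What the plan says.** The SAP synopsis states that "Dialysis type and region are considered to be stratification factors that are potentially prognostically important", and that after stratification "subjects will be randomized 1:1 to receive oral daprodustat or rhEPO". Section 10.10.2 gives the general position: "The prognostic stratification factors (i.e., dialysis type and region) will be taken into account within the analysis models".

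Section 10.10.1 sets the subgroup model for the co-primary and principal secondary endpoints: "Statistical models (Cox Proportional Hazards or ANCOVA) will be adjusted for the covariates used in the original analysis, subgroup, treatment and treatment by subgroup interaction". It then makes an exception for the *Regions combined* subgroup (USA, non-USA), where "the randomization stratification factor Region (with 5 levels, Regions 1- 5) will not be included in the statistical model". Later in the same section a general rule covers any subgroup category that measures the same or a similar thing as a prognostic stratification variable, with country given as the example: in that case "the randomization stratification variable will be removed from the model".

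Section 10.9.1 defines five regions, and Region 5 is the USA alone. The covariate table in 10.10.1 applies the USA/non-USA subgroup to both co-primary endpoints and to the principal secondary safety and efficacy endpoints. On reporting, "Point estimates and two-sided 95% CIs will be estimated within subgroups". Consistent direction and a non-significant interaction p-value, judged at a two-sided 10% level, are taken as support that the overall effect applies to the whole study population.

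**The concern.** USA/non-USA is a coarser version of Region, not a substitute for it. It carries one of Region's four degrees of freedom. The other three, the differences among the four non-USA regions, leave the model even though treatment was allocated within those regions.

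After stratified allocation, omitting a prognostic stratum from an ANCOVA puts between-stratum variation into the error term. The estimate keeps its actual precision, but the reported standard error overstates its variability. For most purposes that is harmless conservatism. Here the plan reads a non-significant interaction as evidence of consistency, so an oversized standard error leans toward the reassuring conclusion.

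**Working it through.** The SAP states no standard deviation, regional difference, subgroup size or interval width for this subgroup, so there is no figure of its own to reproduce. The steps below check the structure and then size the effect under stated assumptions.

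**1. Was removal necessary?** A design with five Region indicators, a USA indicator, treatment, treatment by USA and baseline has 9 columns and rank 8. One column is redundant because the USA indicator repeats Region 5. The treatment differences within USA and within non-USA remain estimable, so dropping Region was one way to clear the redundancy but not the only one.

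**2. Interval width.** The ratio of width with Region omitted to width with Region kept is 1/√(1 − R²). Here R² is the partial R-squared of Region within USA/non-USA, after baseline value and dialysis type.

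| Partial R² (assumed) | Extra width |
|---|---|
| 0 | 0% |
| 1% | 0.5% |
| 2% | 1.0% |
| 5% | 2.6% |
| 10% | 5.4% |
| 20% | 11.8% |

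**3. Simulation.** Assumed inputs: 3,000 subjects, 28% in the USA, 1:1 allocation within region, residual SD 1, one baseline covariate, 1,000 runs per setting. Entries are average model standard errors.

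| Non-USA regional means (USA 0) | Non-USA: dropped / kept | USA: dropped / kept |
|---|---|---|
| no differences | 0.0430 / 0.0430 | 0.0690 / 0.0690 |
| −0.2, −0.1, 0.1, 0.2 SD | 0.0434 / 0.0430 | 0.0695 / 0.0690 |
| −0.5, −0.2, 0.2, 0.5 SD | 0.0448 / 0.0430 | 0.0718 / 0.0690 |

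In the widest setting the non-USA interval is 0.0448/0.0430 = 1.042 times as wide. The empirical standard deviation of the non-USA estimate is 0.0424 under both models, and coverage with Region dropped is about 96%. The USA row widens too, although it is a single region, because the model pools the residual variance.

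**4. Interaction test, widest setting.**
- Standard error with Region kept: √(0.0430² + 0.0690²) = 0.0813.
- Standard error with Region dropped: √(0.0448² + 0.0718²) = 0.0846.
- Ratio: 0.0846/0.0813 = 1.041.
- If the true sampling SD matches the kept-Region value, a nominal two-sided 10% test runs at 2 × [1 − Φ(1.645 × 1.041)], which is about 8.7%.

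**5. Cox models.** With an assumed log-hazard spread of 0.6 across regions, about 530 events and a true hazard ratio of 0.8 (60 simulated trials), the mean hazard ratio was 0.799 without Region and 0.792 with it, at the same standard error. Keeping Region brings no material gain for the time-to-event endpoints.

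**The case against.** The strongest reply is that the removal is deliberate and pre-specified. The sentence on *Regions combined* applies the general rule in 10.10.1 for overlapping variables, and the overlap is real. A reader might infer a contradiction with 10.10.2, but the documents do not support that: 10.10.2 is the general statement, and 10.10.1 sets explicit exceptions to it. A reader might also infer that regional adjustment disappears entirely. It does not, because the USA/non-USA contrast remains as the subgroup term.

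The size of the effect is also open. The SAP calls region only potentially prognostic. Baseline Hgb or baseline IV iron dose stays in the respective model, and both arms are dosed by algorithm to a common Hgb target, which may leave little regional spread in Hgb. Subgroup results are described as consistency checks that may have low power and are not adjusted for multiplicity. The five-level Region subgroup is reported separately as well.

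All of this stands and keeps the point small. It does not remove it. A rule that makes sense when the subgroup replaces the stratification factor, as country does for region, fits poorly when the subgroup replaces only part of it.

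**Conclusion.** The point holds as a minor precision issue for the Hgb and IV iron rows of one subgroup. Three degrees of freedom of a randomization factor are left unadjusted without need. The resulting intervals are conservative, and the interaction test runs below its nominal level, only as far as region is prognostic after the other covariates. For a partial R-squared of 1% to 10% the widening is about 0.5% to 5%; if region is not prognostic it is zero. These figures rest on assumed regional differences and subgroup shares. They describe a single completed data set, before imputations are combined.

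It would be tempting to say that the intervals are wider than the design warrants, or that the subgroup estimates are biased. The first is conditional on something the SAP does not quantify. The second is wrong for the linear models under stratified 1:1 allocation. The co-primary analyses and the Holm-controlled tests are unaffected.

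**What to change.** Make two edits in SAP section 10.10.1:

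- Replace the sentence on *Regions combined* with one stating that Region is kept, nested within USA/non-USA (four levels in non-USA, one in USA), alongside treatment, USA/non-USA and their interaction. Nesting clears the redundancy and leaves both within-subgroup treatment differences estimable.
- Limit the general removal rule to subgroups that fully replace the stratification factor, such as Region itself or country. Deleting the *Regions combined* sentence alone would not be enough, because the general rule would still take Region out.

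The cost is three model degrees of freedom and two sentences. No other analysis changes.
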